9.4.2 Reporting of (Serious) Adverse Events and other safety related events

In accordance with Art. 37, Art. 42, Art. 43

9.4.3 Follow up of (Serious) Adverse Events

A safety-related event is logged and immediately reported to the sponsor investigator (head of the research laboratory), who is also the study leader, and the supervisor of the study.

SUPSI

The CEC will be informed as soon as possible and appropriate changes will be made to the protocol of the study. Further explanations can be found in chapter 2.10. Safety and protective measures must be reported to the responsible CEC within two days.

The report continues to the business liability insurance (Basler Versicherung) of Thim van der Laan AG in Landquart.

9.5 Medical Device Category A studies

-

9.5.1 Definition and recording of safety-relevant events

-

9.5.2 Reporting of Safety related events

-

9.5.3 Notification of a security-relevant event

-

SUPSI

10 STATISTICAL METHODS

10.1 Hypotheses & Factors

Mobilization of the patella in the caudal / cranial direction by the patello – repetitive mobilizations versus one-time mobilization Objective displacement of the patella:

H0 The patella does not shift significantly more during repetitive mobilizations than during a single mobilization by the patello.

H1 The patella shifts significantly more during repetitive mobilizations than during a single mobilization by the patello.

Subjective well-being of the subject:

H0 Subjective well-being does not change significantly more with repetitive mobilizations than with a single mobilization by the patello.

H1 Subjective well-being changes significantly more with repetitive mobilizations than with a single mobilization by the patello.

A 2-factor analysis is carried out.

Factor 1: Intervention

Factor 2: Time intervention: Start (pre-intervention, 1st measurement), after a single mobilization (2nd measurement), after 10 (3rd measurement), after 20 (4th measurement), after 30 (5th measurement), after 50 mobilizations (6th measurement)

Sample size

The planned sample size is $n = 30$ subjects. This size is expedient, time-wise and financially feasible for the study.

10.2 Criteria for the statistical use of data in the case of incomplete data sets

A complete mobilization interval must be completed for the data to be included in the study. If a mobilisation interval (e.g. interval '20 mobilisations', but termination after 15 mobilisations) has to be interrupted, only the previously collected complete mobilisation interval data can be used. This ensures that all data remains homogeneous and comparable. No substitute is sought for the missing mobilization interval data.

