5.2 Secondary outcomes

Subjective information on general well-being

The secondary outcome, the recording of the subjective well-being of the test person, is determined using a visual analogue scale (VAS scale 0 - 10) and reflected in the number of cm. The value "0" describes "maximum feeling of well-being", the value "10" a "maximum feeling of discomfort". The value is considered a subjective parameter.

Security considerations

SUPSI

No further results are recorded that would serve safety.

Discontinuation of the experiment is the responsibility of the examiner with regard to the subject's subjective feelings and expressions.

If a test subject does not feel comfortable during the intervention according to his or her subjective assessments, he or she can discontinue the experiment and withdraw participation in the study without any disadvantages.

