9.1.3 Measurement of secondary outcomes

Using a visual analogue scale, which goes from 0 – 10, subjective well-being is asked directly after the mobilisation intervals. The value "0" stands for "maximum well-being" and the value "10" for "maximum discomfort". The values are transferred to the data sheet.

SUPSI

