9.2.3 Sequence of the measurements

After determining the contact pressure, the pre-mobilization measurement is carried out (**1st measurement**). The ultrasound probe is used to visualize a reference point on the patella and at the same time the lateral femoral epicondyle on the thigh and save it as an image. Afterwards, the mobilization pressure is built up individually up to the tolerance limit of the test subject so that a displacement of the patella caudally takes place. The maximum deflection of the patella to the reference point on the thigh is determined, the device settings are noted and transferred to the data sheet (**2nd measurement**).

As described above, further measurements are carried out according to the following scheme: after 10 mobilisations (**3rd measurement**), after 20 mobilisations (**4th measurement**), after 30 mobilisations (**5th measurement**) and after 50 mobilisations (**6th measurement**).

Table 5: Overview of the course of studies

Time	Preparation	Pre	1 Mob.	10 Mob.	20 Mob.	30 Mob.	50 Mob.
Time (min)		5	10	20	30	40	50
Measurement		1.	2.	3.	4.	5.	6.
Subject information	X						
Consent	X						
Demographics	X						
Intervention			X	X	X	X	X
Ultrasound image		X	X	X	X	X	X
Subj. Well-being		X	X	X	X	X	X

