10.3 Planned analyses

10.3.1 Datasets and Data Population

Only complete mobilization interval datasets will be included in the study and integrated into the analysis. No new test subject is being sought to replace the missing data.

SUPSI

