10.4 Drop-outs and Missing Data

If a subject wishes to withdraw from the study before the end of all measurement days and interventions, or if he or she has to be excluded by the study leader due to an event, the complete mobilization interval data collected up to that point will be included in the data analysis.

No replacement of test persons is being sought for the missing data sets.

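### If a subject stops for discomfort, the complete-interval rule discards that subject's VAS for the interval and tilts the single-versus-repetitive well-being comparison towards better tolerability

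*Combined protocol and SAP*

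**What the plan says.** Section 10.2 takes the case of a stop after 15 mobilisations in the 20-mobilisation interval and rules that "only the previously collected complete mobilisation interval data can be used". Section 10.3.1 makes this the dataset definition: "Only complete mobilization interval datasets will be included in the study and integrated into the analysis". Section 10.4 applies it to drop-outs: "the complete mobilization interval data collected up to that point will be included in the data analysis". All three are written for the data as a whole and do not separate displacement from the VAS.

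After the pre-mobilisation score, the VAS is tied to completed intervals: "subjective well-being is asked directly after the mobilisation intervals" (section 9.1.3). The scale runs from 0 (best) to 10 (worst).

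On stopping, section 5.2 says: "Discontinuation of the experiment is the responsibility of the examiner with regard to the subject's subjective feelings and expressions". A subject who feels uncomfortable may also end the session: "he or she can discontinue the experiment and withdraw participation in the study without any disadvantages". Section 9.2.3 explains how the load is set: "the mobilization pressure is built up individually up to the tolerance limit of the test subject". Section 8.3 then keeps that setting for the measurements.

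The second hypothesis pair in section 10.1 compares the change in well-being under repetitive mobilisation with that under a single mobilisation. Section 10.3.2 names a repeated-measures MANOVA and no method for missing data. No further results (9.1.4), no safety parameters beyond the health questionnaire (9.1.5), no secondary analysis (10.3.3) and no safety analysis (10.3.5) are planned.

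**The concern.** For displacement the rule is sensible: a measurement labelled 20 mobilisations should follow 20 mobilisations. For the VAS it makes inclusion depend on the value being measured. Someone who stops at 15 of 20 because of discomfort would probably have given a high score, and that interval is excluded together with all later ones. The same subject's score after a single mobilisation is kept. The late scores then come from those who tolerated the procedure, and the comparison in section 10.1 leans towards repetition being no worse than one mobilisation.

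At stake is the only subject-reported outcome in a pre-market device study. The results would give no sign of the problem, because neither the number of stops nor their reasons are planned for reporting. A stop-time score that was not collected cannot be recovered later.

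**Working it through.** **The plan's own figure.** The documents give no VAS mean, SD or stop rate. The only relevant figure is the synopsis power of 0.95 for n = 30 and effect size 0.68. A paired t-test, two-sided at 0.05, with 29 degrees of freedom and noncentrality 0.68 × √30 = 3.72, gives 0.949, so it reproduces. It makes no allowance for stops: at the same effect size, power is 0.925 with 27 subjects and 0.891 with 24. That figure is not in dispute here.

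**Step 1: the mean at one interval.** Let k of 30 subjects stop, let M be the completers' mean, and let the stoppers' VAS lie a gap above M.

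- All 30 subjects: [(30 − k)·M + k·(M + gap)]/30 = M + (k/30)·gap.
- Under the plan: M.
- Understatement: (k/30)·gap.

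| Stops k | gap 2 | gap 4 | gap 6 |
|---|---|---|---|
| 0 | 0 | 0 | 0 |
| 1 | 0.07 | 0.13 | 0.20 |
| 3 | 0.20 | 0.40 | 0.60 |
| 6 | 0.40 | 0.80 | 1.20 |

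Both k and gap are assumptions.

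**Step 2: the contrast that the hypothesis concerns.** Section 10.1 is about change from the single mobilisation, so step 1 is not enough. I take the method in section 10.3.2 to apply to the VAS as well. The plan does not settle who enters it: section 10.4 keeps partial data, whereas a repeated-measures MANOVA in its usual form needs every time point. Both readings were simulated.

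Assumed inputs: 30 subjects, one measurement day, six measurements, 3,000 runs per scenario, VAS SD 2, correlation 0.6, starting mean 3, scores limited to 0–10. The worsening builds up from measurement 2 to measurement 6. A subject stops in the first of measurements 3–6 at which the VAS would reach the threshold, and contributes nothing from there on. The last three columns give the mean change from 1 to 50 mobilisations.

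| Worsening set | Threshold | Stopping | True change | Available data | Subjects with a gap dropped |
|---|---|---|---|---|---|
| 0 | 7 | 6.5% | −0.003 | −0.206 | −0.035 |
| 0 | 8 | 2.0% | 0.004 | −0.070 | −0.007 |
| 0 | 9 | 0.5% | 0.008 | −0.013 | 0.005 |
| 1 | 7 | 12.2% | 0.957 | 0.573 | 0.870 |
| 1 | 8 | 4.2% | 0.957 | 0.801 | 0.921 |
| 1 | 9 | 1.2% | 0.961 | 0.907 | 0.948 |
| 2 | 7 | 22.0% | 1.955 | 1.280 | 1.763 |
| 2 | 8 | 9.4% | 1.940 | 1.608 | 1.843 |
| 2 | 9 | 3.2% | 1.936 | 1.805 | 1.897 |

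The available-data bias is larger because stoppers tend to score high after one mobilisation too. Their early score stays in while their late score leaves, so a false improvement of 0.21 appears even with no true change (6.5% stopping). Dropping stoppers altogether removes most of that, at a cost in power: 0.825 to 0.719 in the scenario with 12% stopping.

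**The case against.** The best case for the plan is that the problem may not arise. Subjects are healthy, aged 18–30, and excluded if they fear the intervention (section 7.1), and section 3.7 rates the risk as small. With no discomfort stops the bias is zero, and at about 1% stopping it is slight. This stands, and it limits the point to a conditional one.

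Second, pressure is built up to the limit before the second measurement, so the single-mobilisation score is also taken at the limit. Stoppers may already score high there, and their further change may be modest. This also stands. It is why the single-interval figures must not be read as bias in the contrast, and why the bias is only about 0.09 (0.957 − 0.870) at 12% stopping when stoppers are dropped.

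Third, the rule has a stated purpose, comparability, and a score after 15 mobilisations is not a score after 20. That justifies the rule for displacement. For the VAS it is a reason to label the stop-time score, not to lose it.

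A reader might infer more than the documents support:

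- *The VAS is never asked at a stop.* The documents do not provide for it, but they do not forbid it. The point survives because section 10.2 would exclude such a score anyway.
- *Stops are for discomfort.* It is one ground. Section 10.4 also covers any wish to withdraw and exclusion after an event.
- *The VAS is the only record of poor tolerability.* Sections 9.1.6 and 9.4.1 require an incident record for injuries and side effects. That record is not an analysed outcome, however, and plain discomfort need not enter it.

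**Conclusion.** The mechanism follows from the text: for the VAS, exclusion can depend on the discomfort being measured, and no planned analysis would reveal it. The direction, towards better tolerability, was the same in all nine simulated scenarios under both readings of the analysis.

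The size is not known and depends on assumed stop rates and gaps. It runs from zero with no stops to 0.40–1.20 points in a single-interval mean with six. For a true change of about 0.96, the loss is 0.05 to 0.38 points with available data at 1–12% stopping, and 0.01 to 0.09 if subjects with a missing interval are dropped.

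It would go too far to say that the trial will report the device as better tolerated than it is, or to fix a single figure. For example, completers at 4 and stoppers at 9.5 give (3/30) × 5.5 = 0.55 or (6/30) × 5.5 = 1.10. Those are single-interval means at high assumed inputs, not the comparison in section 10.1. The point concerns a secondary outcome and leaves the displacement result untouched. It is worth acting on because the remedy is cheap and the missing scores cannot be collected afterwards.

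**What to change.** 1. In sections 10.2, 10.3.1 and 10.4, limit the complete-interval rule to displacement.
2. When an interval is interrupted, ask the VAS at that moment and record it with the number of mobilisations completed and the reason for stopping.
3. Beside the VAS results, report the number of discomfort stops at each interval.
4. Add a sensitivity analysis that enters the stop-time VAS, or a worst-case score, for the interrupted interval and for every later missed interval on that measurement day. Filling only the interrupted interval would leave the later means to completers and would not keep most stoppers in a repeated-measures analysis.
5. State in section 10.3.2 whether subjects with a missing interval stay in the main analysis, since the size of the bias depends on it.

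The cost is one question and two data-sheet fields for subjects who stop, plus one analysis. The VAS is already asked orally and written on the sheet (section 11.2.1). No device setting or stopping rule changes. The stop-time score reflects fewer mobilisations than the nominal interval, and carrying it forward is an assumption, so it belongs in a sensitivity analysis and not in the main result.

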10.3 Planned analyses

10.3.1 Datasets and Data Population

Only complete mobilization interval datasets will be included in the study and integrated into the analysis. No new test subject is being sought to replace the missing data.

SUPSI

10.3.2 Primary Analysis

The statistical data analysis is carried out by the statistician after completion of the data collection of the entire project.

Repeated measures analysis of variance (MANOVA) A 2-factor analysis is performed.

Factor 1: Intervention

Factor 2: Time intervention: Start (pre-intervention, 1st measurement), after a single mobilization (2nd measurement), after 10 (3rd measurement), after 20 (4th measurement), after 30 (5th measurement), after 50 mobilizations (6th measurement)

The significance level is set at $P < 0.05$, and the statistical data analysis is carried out with SPSS V. 24.

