Background and Rationale:	Restricted movement of the knee joint hinders the everyday life of the affected person. They can be caused by osteoarthritis or after surgical procedures on the knee joint. The therapy of choice for limited knee mobility is the active and passive mobilization of the knee joint (Art. Genu, Art. Patellofemorale, Art. Tibiofibulare) with involvement of the soft tissue mantle (muscles, connective tissue). Active mobilization is carried out by the patient independently through a specific exercise program. Passive mobilisation is part of physiotherapeutic treatment. The aim of mobilisation is to activate the formation of synovial fluid, to regulate the tone of the muscles and to influence the fibre alignment of the collagen tissue. The Patello device was built to perform passive, continuous mobilization of the patella as part of rehabilitation with limited knee mobility. The area of application and indication is based on the widely used "Kinetec" knee and hip mobilisation splint. What is innovative about the Patello is that only the Art. patellofemoral is mobilized; the patella is moved on its plain bearing in the cranial and caudal directions.
Objective(s):	The aim of this clinical trial is to prove the effectiveness of the patello.
Outcome(s):	Primary outcome: Objectification of the displacement of the patella to cranial and caudal measurement with an imaging ultrasound device (esaote MyLabClassicC, Genoa, Italy, www.esaote.com). Secondary outcome: Subjective well-being of the subject measured by a visual analogue scale (VAS scale 0 - 10). The knee to be tested is determined by lot (randomized) per test person. The outcomes are recorded after 1, after 10, after 20, after 30 and after 50 mobilizations in the caudal deposition position. The entire measurement procedure is carried out 2x in a week per test subject with a 2-day break in between.
Study design:	Clinical effectiveness study

SUPSI

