	
Examiner
 
- [name]^{1,2}- [name], Drs.^{1,2}- [name], MSc¹- [name] 
¹ University of Applied Sciences and Arts Southern Switzerland SUPSI, Department of Business Economics, Health and Social Care, Physiotherapy Graubünden, [name]
 
² THIM University of Applied Sciences in Physiotherapy, [name]
 
³ Medical Center Bad Ragaz, [name]

Investigator(s):	
Contact / Director of Studies
 
[name], PhD
 
University of Applied Sciences and Arts Southern Switzerland (SUPSI) Department of Business Economics, Health and Social Care Physiotherapy Graubünden [name] [contact] [contact]

Study Centre(s):	Single Centre Study: Rehabilitation Research Laboratory University of Applied Sciences and Arts Southern Switzerland SUPSI Department of Business Economics, Health and Social Care Physiotherapy Graubünden [name]
Statistical Considerations:	
Patellar displacement during mobilization application by the patello. Repeated measures analysis of variance (MANOVA)
 
A 2-factor analysis is carried out.
 
Factor 1: Intervention Patello
 
Factor 2: Time intervention: Start (pre-intervention, 1st measurement), after a single mobilization (2nd measurement), after 10 (3rd measurement), after 20 (4th measurement), after 30 (5th measurement), after 50 mobilizations (6th measurement).
 
The significance level is set at $P < 0.05$, and distatistical data analysis is carried out using the Statistical Package for Social Sciences (SPSS V. 24) from IBM, New York, USA.

SUPSI

GCP Statement:	This study will be conducted in compliance with the protocol presented here, the current version of the Declaration of Helsinki, the ICH-GCP, ISO EN 14155 (where applicable), and the Swiss Human Research Ordinance HFV.
-----------------------	--

SUPSI

Overview of the study

Knee joint mobility can be limited by arthritic or post-operative functional or structural changes. Reduced knee joint mobility can interfere with the affected person's everyday activities. Active movement of the knee promotes the formation of synovial fluid, which is essential for the supply of cartilage tissue. Passive mobilization techniques as part of a physiotherapeutic treatment release structural blockages and favor the fiber alignment of the collagen tissue.

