6.1 Method for minimizing influencing factors

6.1.1 Randomization

Randomization is used to randomly determine the application side, left or right knee.

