7.3 Group assignment

SUPSI

There will be no group assignment.

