8.1.2 Control intervention

No control intervention is carried out.

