8.2.2 Control intervention

There is no control intervention.

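### Factor 1 (Intervention) has no stated levels in a one-group design, and measurement day is in no factor, so the between-day objective has no planned analysis

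*Combined protocol and SAP*

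**What the plan says.** The model is announced in three places. Section 10.3.2 has "Repeated measures analysis of variance (MANOVA) A 2-factor analysis is performed", section 10.1 has "A 2-factor analysis is carried out", and the synopsis (Statistical Considerations) has "Factor 1: Intervention Patello". Each lists six levels for Factor 2: before mobilisation and after 1, 10, 20, 30 and 50 mobilisations. None lists any level for Factor 1.

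The design has a single condition. Section 8.1.2 states "No control intervention is carried out", section 8.2.2 states "There is no control intervention" and section 7.3 states "There will be no group assignment". The lot decides only the knee: "Randomization is used to randomly determine the application side, left or right knee" (6.1.1).

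On repetition, the synopsis (Outcomes) says "The entire measurement procedure is carried out 2x in a week per test subject with a 2-day break in between". Sections 4.3 and 9.2.4 give the reason, which is to see whether an effect lasts or builds up. Both pairs of hypotheses in section 10.1 compare repeated with single mobilisation and do not mention days. Section 10.3.3 lists no secondary analysis. Sections 10.3.1 and 10.4 bring completed mobilisation intervals into the analysis, and 10.4 does so explicitly for people who leave before all measurement days are done.

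**The concern.** A two-factor analysis needs at least two levels of each factor. Intervention appears to have one, so the model as written cannot be run with two working factors. The variable that does have two levels within each participant, and that carries a stated objective, is measurement day, and it is absent from the model.

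Two things are at stake. First, the between-day part of the objective in 4.3 and 9.2.4 has no planned answer, although every participant attends twice for it. Second, the analyst must decide after the data are in whether the days are pooled, averaged, analysed separately or compared. Section 10.3.6 has departures from the planned analysis recorded and justified, but a day analysis cannot depart from a plan that contains none.

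**Working it through.** The point disputes no number in the plan. The synopsis figure (n = 30, effect size 0.68, power 0.95) is not tied to day or to any named factor, and plays no part in what follows.

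**Inputs.** Participants: 30 (section 10.1, sample size paragraph). Factor 1 levels: none stated. Factor 2 levels: m = 6 (10.1, 10.3.2). Sessions per participant: 2 (synopsis, 4.3, 9.2.4). Intervention conditions: 1 (8.1.2, 8.2.2, 7.3).

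**Step 1: look for a second level of Factor 1.**

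- Control or second group: excluded by 8.1.2, 8.2.2 and 7.3.
- Before versus after mobilisation: already inside Time, whose first level is the pre-mobilisation measurement.
- Left versus right knee: two levels, but between participants. It is not an intervention and is not named as a factor.
- Day 1 versus day 2: two levels within participants, which would make a 2 x 6 design. No section says that Factor 1 means day.

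**Step 2: degrees of freedom.** With k levels of Factor 1 and m = 6 times, the effects have k - 1, m - 1 and (k - 1)(m - 1) degrees of freedom. Error terms assume complete data, sphericity and one value per cell.

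| Effect | k = 1 (Intervention, one level) | k = 2 (Day) |
|---|---|---|
| Factor 1 | 1 - 1 = 0 | 2 - 1 = 1 (error 29) |
| Time | 6 - 1 = 5 (error 29 x 5 = 145) | 5 (error 145) |
| Factor 1 x Time | 0 x 5 = 0 | 1 x 5 = 5 (error 145) |

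With one level, the two-factor model is the one-factor Time model.

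**Step 3: readings against cells.** Each participant gives 2 x 6 = 12 readings. The written factors define 1 x 6 = 6 cells, so each cell receives two readings that the model cannot tell apart. The rank of the design for the 12 readings is 6 with a constant factor and 12 with Day. For the VAS this is 30 x 2 x 6 = 360 planned readings, of which 30 x 6 = 180 fall on day 2.

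**Step 4: what happens to displacement.** The text allows two analysed values. Sections 9.1.2 and 9.2.3 can be read as a patella-to-epicondyle distance at each of the six measurements. They can also be read as a displacement relative to the same day's measurement 1. On the second reading measurement 1 carries no information, which leaves 2 x 5 = 10 values per participant (30 x 10 = 300 in all) and Day, repetition and interaction with 1, 4 and 4 degrees of freedom. The plan does not say which is meant, so the repair must cover both.

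**Step 5: objective against analysis.** Build-up within a session is covered by Time. A difference between sessions appears in no hypothesis (10.1), no factor (10.3.2) and no secondary analysis (10.3.3).

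**The case against.** The strongest reply is that this is an undefined label, not a broken analysis. The zero degrees of freedom follow only if Factor 1 has one level, and the design does contain two two-level variables, side and day. The hypothesis in 10.1 is a contrast within Time and survives whatever Factor 1 means. Section 9.2.4 asks only for a practical statement about possible effects, which a descriptive comparison of days might supply. All of this stands, and it limits the point. It does not supply the missing definition, and it does not say how the two days are handled.

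Three stronger readings are tempting, and the documents do not support them.

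- A reader might infer that the day-2 data, half of the total, are unused or discarded. Sections 10.3.1 and 10.4 include completed intervals from the measurement days. What is missing is a model term, not a use.
- A reader might infer that the primary hypothesis cannot be tested. Repeated against single mobilisation is a contrast among the levels of Time and remains estimable.
- A reader might infer that 30 participants are too few to detect a day effect. The documents give neither a standard deviation nor a target day difference, so adequacy can be neither claimed nor denied.

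It is also fair to warn against a careless repair. Removing measurement 1 from the displacement analysis in every case would lose the comparison closest to the aim of showing that the device moves the patella (Overview of the study; 4.1). Referring every value to the same day's start would also subtract any shift in resting position carried over from day 1.

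**Conclusion.** The point holds. Factor 1 is undefined in all three places where the model is given, and the one-group design offers no second intervention level. With one level, two of the three effects in the announced model have 0 degrees of freedom. Independently of how that label is read, measurement day has no term, hypothesis or secondary analysis. The between-day part of the objective in 4.3 and 9.2.4 therefore has no planned analysis, and 12 readings per participant meet 6 defined cells.

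This should be fixed, but it does not undermine the within-session hypothesis. The degrees-of-freedom result rests on reading Intervention as a single condition. The error terms assume complete data and sphericity. The size of any between-day effect is unknown from the documents, so no numerical consequence is attached to it.

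**What to change.** In the synopsis, 10.1 and 10.3.2, replace the Intervention factor with *Factor 1: Measurement day (1, 2), within participant*. Then:

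- **Factor 2.** Keep all six measurements where the analysed value is the patella-to-epicondyle distance or the VAS. If it is displacement relative to the same day's measurement 1, use measurements 2 to 6 and add a test that displacement after the first mobilisation differs from zero.
- **The 10.1 test.** State that it is the contrast of measurements 3 to 6 against measurement 2, and whether it is averaged over days.
- **Section 10.3.3.** Name the Day effect and the Day x Time interaction as the between-day analysis, with confidence intervals, or state that the day comparison is descriptive. If a carried-over shift is of interest, include the day-2 minus day-1 difference in pre-mobilisation distance.
- **Device settings.** The aim-of-study text in chapter 3 and section 3.6 have settings redefined on each measurement day. The synopsis (Measurement procedure) and section 8.3 have them held for all of a participant's measurements. These passages must be reconciled, because they decide whether a day difference can be interpreted.

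The cost is a small amount of extra analysis and no new participant data. The pre-mobilisation distance may need stored images to be measured again, since the data sheet holds displacement in mm (11.2.1). Because the analysis plan sits in the protocol, the change needs review by, or notification to, the ethics committee and Swissmedic (2.3, 2.10).
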